⁹⁹Tc-MDP in Postmenopausal Women With Differentiated Thyroid Cancer and
Osteoporosis

Trial registration: NCT02304757

April 16, 2021

Study Protocol

Study Type: Interventional

Study Design: Treatment, Parallel Assignment, Single Blind (Outcomes Assessor), Non-Randomized, Efficacy Study

Patients recruitment

This was an open-label, prospective non-randomized study carried out in three centers (ClinicalTrials.gov ID: NCT02304757) from November 2015 to December 2019. Postmenopausal women are eligible in the study fulfilling all the following criteria. (1) They were pathologically diagnosed with DTC including papillary or follicular carcinoma. (2) They received a near total thyroidectomy and radioiodine treatment. (3) TSH suppression should be at least one year before the study. (4) Bone mineral density (BMD) in lumbar spine and/or hip was tested by Dual-energy X-ray absorptiometry (DXA) at baseline, 6 month (m) and/or 12m follow up. 5) The diagnosis of osteoporosis was T-score ≤ -2.5 SD at the lumbar spine, or hip.

We excluded patients considering the following criteria: (1) patients having medications for OS before TSH suppression treatment; (2) secondary OS; (3) severe liver or kidney disease; (4) myelosuppression; (5) digestive disease; (6) long term use of immunosuppressive agent, estrogen or estrogen receptor modulators. This study was approved by the Institutional Review Board of Hospital Research Ethics. All the patients were fully acquainted with their treatment and consented to participate in the clinical trial.

TSH suppression treatment

TSH suppression treatment was based on the risk stratification of DTC using levothyroxine (L-T₄) as recommended

Treatment protocol for osteopenia and osteoporosis

Patients with OS were divided into ⁹⁹Tc-MDP and alendronate treatment groups.

1. ⁹⁹Tc-MDP treatment group: 15mg ⁹⁹Tc-MDP were intravenously administered twice a week for 10 weeks, then once a week for 8 weeks, every two weeks for 22

weeks and monthly for another 3m.

2. Alendronate treatment group: 70mg alendronate (Merck & Co., Darmstadt, Germany) was administered orally once a week for 12m.

Laboratory assays

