Bone alkaline phosphatase (ALP), osteocalcin and propeptide of type I procollagen (PINP), and C-terminal telopeptide of type I collagen (CTX) were all determined by enzyme-linked immunosorbent assay (Modular E170, Hoffmann-La Roche, Basel, Switzerland). Free T₃, free T₄, thyroid stimulating hormone (TSH) was measured using a time-resolved immunofluorometric assay (Anytest, sym-bio lifescience co., ltd, Shanghai, China). 25(OH) D, parathyroid hormone (PTH), serum calcium and phosphorus and other laboratory tests were measured as routine at baseline and 12m.

Analysis of knee relief, QOL and adverse reaction

Lysholm knee (LYS) rating scale was used to evaluate the knee function at baseline and 12m. QOL in patients with OS was measured with a 36-item Short Form Health Status Survey questionnaire (SF-36) at baseline and 12m. SF-36 including four physical and fundamental items were calculated which represent the deviation from the reference population. The higher score by SF-36 and LYS means a better QOL and knee function. A treating physician reviewed the clinical results and any discomfort at each visit.

Statistical Analysis Plan

The predetermined primary end point was the difference in the change in BMD of the lumbar spine between the two groups. Sixty four sample size was assumed to achieve 80% power to detect non-inferiority using a one-sided two sample t-test. The margin of non-inferiority is 0.5% percent. The true difference between the means is assumed to be 0. The significance level (alpha) of the one sided test is 0.025. The data were drawn from population with standard deviations of 0. Consider the 10% loss of

follow-up rate, group sample size was 70 cases.

Continuous data are expressed as the mean \pm standard deviation. Independent sample t-test by SPSS 22 was used to compare the basic information, clinical characteristics within groups at baseline and the difference values of BMD between that at baseline and 6m and 12m after treatment. Differences in BMD, QOL by SF-36 questionnaire, bone turnover marks and other laboratory results were determined using a paired t-test (one-sided tests) and Mann-Whitney U test. A Fisher exact test was used to compare the adverse events. Pearsman Rho was used to analyze the correlation of lumbar uptake of Na^{18}F and BMD/T value by DXA. P value <0.05 was considered statistically significant.

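### Laboratory results and adverse events are analysed only by group-level tests, with no per-woman abnormality counts and no risk differences with confidence intervals, so the analysis could not support a conclusion of no safety difference

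*Combined protocol and SAP*

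**What the plan says.** Under Laboratory assays, the schedule for these tests is: "serum calcium and phosphorus and other laboratory tests were measured as routine at baseline and 12m". Under Statistical Analysis Plan, the method is: "other laboratory results were determined using a paired t-test (one-sided tests) and Mann-Whitney U test". The same sentence also covers BMD, SF-36 and bone turnover markers. The descriptive summary is a mean with its standard deviation ("Continuous data are expressed as the mean").

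Adverse events get one sentence: "A Fisher exact test was used to compare the adverse events". The only criterion is: "P value <0.05 was considered statistically significant".

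The section headed Analysis of knee relief, QOL and adverse reaction adds review of individual patients: "A treating physician reviewed the clinical results and any discomfort at each visit".

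The plan does not give:
- a direction for the one-sided test;
- a count of women outside a reference range;
- the unit for adverse events (women or events);
- an incidence or risk difference with a confidence interval.

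**The concern.** Laboratory toxicity often appears as a few patients crossing a limit while the rest do not move. A test of mean change dilutes those few across the whole group, and a rank test caps how much each of them can contribute. If the one-sided test points the wrong way, it cannot detect the harm at all.

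The Fisher test is valid, but at a sample size set for BMD it has little power for uncommon events, and a P value alone does not show how large a difference remains possible.

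At stake is what the report can say. As planned, the analysis could yield statements of no significant laboratory change and no significant adverse event difference even if several women had marked abnormalities, and readers would have no count or interval by which to judge them. Organ function matters to this trial's own entry rules, which exclude "3) severe liver or kidney disease; (4) myelosuppression; (5) digestive disease".

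**Working it through.** **Group size.** The plan gives no figure for safety power or precision. Its only sample size is 64, raised to a group size of 70, for lumbar BMD. I read 64 as per group because the 70 is described as a group size.
- The printed SD of 0 makes the formula return 0, so 64 does not follow from the printed inputs. That is a separate matter and may be lost text.
- With an assumed SD of 1.0, n = 2 × 1² × (1.96 + 0.84)² / 0.5² ≈ 63 per group. The t-based version gives 64.
- Dropout: 64/0.9 = 71.1 and 64 × 1.1 = 70.4, both close to 70.

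Nothing below depends on the SD. Equal groups are assumed.

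**Laboratory tests (assumed: 64 women, 3 shift by 5 SD, the others have standard normal changes).**
- Mean shift = 3 × 5 / 64 = 0.234 SD.
- The shifted women also inflate the variance: 1 + 25 × 3 × 61 / (64 × 63) = 2.13. The standard error is √(2.13/64) = 0.183 and the typical t is 0.234/0.183 = 1.28. The one-sided 5% critical value on 63 df is 1.67.
- Simulation (4,000 runs): significant in 29% if the direction matches the harm and 0% if it is opposite.
- Mann-Whitney: the chance that a woman in the affected group exceeds one in the other is about 0.5 × 61/64 + 1 × 3/64 = 0.523. The null standard error is √(129/(12 × 64²)) = 0.051, so the expected z is 0.023/0.051 ≈ 0.46 against 1.96. Simulation: 7%, close to the 5% expected with no effect.

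The number affected drives the result:

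| Women affected | Shift | Paired, matching direction | Mann-Whitney |
|---|---|---|---|
| 1 | 8 SD | 9% | 5% |
| 3 | 3 SD | 20% | 7% |
| 3 | 5 SD | 29% | 7% |
| 3 | 8 SD | 39% | 7% |
| 5 | 5 SD | 64% | 10% |

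**Adverse events (two-sided Fisher, exact; rates assumed).**
- 5/64 v 0/64: P = 2 × (64·63·62·61·60)/(128·127·126·125·124) = 0.058. With no events in one group, 6 are needed in the other for P<0.05 (P=0.028).
- Power for 5% v 0% is therefore the probability of at least 6 events in 64 at a 5% rate: 10% (14% at 70 per group).
- Power at 64 per group for other rates: 10% v 5%, 10%; 15% v 5%, 36%; 20% v 10%, 27%.
- If 64 were the total (32 per group), power for 5% v 0% would be 0.5%.

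**What an interval adds (Newcombe 95% intervals, used here for illustration; an exact interval need not coincide).**
- 3/64 v 0/64: P=0.244; risk difference 4.7% (−1.8% to 12.9%).
- 5/64 v 0/64: P=0.058; risk difference 7.8% (0.6% to 17.0%).
- 0/64 in one group still allows a true rate up to 1 − 0.025^(1/64) = 5.6% (exact two-sided 95%).

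**The case against.** The strongest reply has four parts.

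1. **No safety claim is planned.** The design is labelled an efficacy study, the one primary endpoint is lumbar BMD, and no safety hypothesis or margin is stated. A reader might infer that a non-significant result will be taken as proof of safety; the documents do not say so. This stands. What remains is that P<0.05 is the only criterion offered, so the analysis cannot show absence of a difference.

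2. **Individual results were reviewed.** A marked abnormality could be recorded as an adverse event and so reach the Fisher test. A reader might infer that serious changes in a few women are lost altogether; the physician review means that does not follow. But no grading, threshold or reporting rule carries the review into a table.

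3. **The laboratory sentence is not a safety sentence.** It also covers efficacy measures. Calcium, phosphorus, PTH and 25(OH)D are ordinary metabolic descriptors in these women, and mean change is a reasonable summary for that purpose. Nor is it right that only means are tested, since Mann-Whitney compares ranks. Both points stand, so per-woman counts are needed only for tests used to judge safety. The rank test does not rescue the plan: it responds to a few extreme values even less than the paired test does.

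4. **Fisher's test is conventional and low power is unavoidable at this size.** True. An interval does not remove the imprecision, but it does show it.

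**Conclusion.** The point holds as an omission with a cheap remedy. It does not touch the primary BMD conclusion. The planned tests have little chance of registering harm in a few women: about 29% or 0% for the paired test depending on its unstated direction, about 7% for Mann-Whitney, and 10% for Fisher at 5% v 0%. A non-significant result from them could not support a conclusion of no safety difference.

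These figures assume 64 per group, 3 women affected, a 5 SD shift and the event rates shown; none of the shifts or rates comes from the documents. With 5 women shifted by 5 SD, a paired test in the matching direction reaches 64%, so the weakness is specific to harm in very few women. Mann-Whitney stays at 10% even then.

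The documents do not support the stronger reading that the plan will declare the treatment safe on a non-significant P value, or that individual abnormalities went unseen.

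**What to change.** Add to the Statistical Analysis Plan:

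- For each laboratory test used to assess safety (name them), tabulate by group the number of women moving from within to outside the laboratory's reference range between baseline and 12 months, separately for high and low.
- Report the number of women in each group with at least one adverse event.
- For both, give the between-group risk difference with an exact 95% CI.
- Make any retained laboratory test two-sided.
- State that P>0.05 is not evidence of equal safety.

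The Fisher P value and the mean-change summaries may stay as descriptive additions.

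The cost is some SAP wording and a few tables from data already collected; the reference ranges have to be obtained from the laboratories, since the documents give none. The intervals will be wide and will not be adjusted for the non-randomised allocation, and the report should say so.

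### For SF-36, turnover markers and laboratory results the plan names a one-sided paired t-test and a Mann-Whitney test without assigning either to a contrast, and provides no baseline-adjusted treatment comparison

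*Combined protocol and SAP*

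**What the plan says.** The design has two parallel, non-randomised groups: "Patients with OS were divided into ⁹⁹Tc-MDP and alendronate treatment groups" (Treatment protocol for osteopenia and osteoporosis).

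The second paragraph of the Statistical Analysis Plan has two sentences that matter here.

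- The first: "Independent sample t-test by SPSS 22 was used to compare" baseline characteristics and "the difference values of BMD between that at baseline and 6m and 12m after treatment". This gives BMD change its own two-sample test, which matches the primary endpoint: "The predetermined primary end point was the difference in the change in BMD of the lumbar spine between the two groups".
- The second takes as its outcomes "Differences in BMD, QOL by SF-36 questionnaire, bone turnover marks and other laboratory results" and says that they "were determined using a paired t-test (one-sided tests) and Mann-Whitney U test". The sentence names no contrast, no outcome scale (12-month value or change), no direction for the one-sided tests and no rule for choosing between the two tests.

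The significance threshold for all analyses is P<0.05. No other sentence names a treatment comparison for SF-36, turnover markers or laboratory results.

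The data are paired within patient. Quality of life uses the "36-item Short Form Health Status Survey questionnaire (SF-36) at baseline and 12m", and under Laboratory assays "other laboratory tests were measured as routine at baseline and 12m". The Lysholm score is also taken at baseline and 12 months but is missing from the list of tested outcomes.

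**The concern.** A paired t-test and a Mann-Whitney test answer different questions. The first asks whether one group changed over time. The second compares two independent samples. Naming them together for one list of outcomes leaves two readings open.

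- **Within-group reading.** BMD appears again in this list although its between-group test has just been given, so the sentence may describe baseline-to-follow-up comparisons, with Mann-Whitney as the rank alternative. The rank counterpart of a paired t-test is the Wilcoxon signed-rank test, which the plan never names. Mann-Whitney would treat a woman's two values as independent.
- **Split reading.** Paired t-test within groups, Mann-Whitney between groups. Each test then fits its data structure, but the treatment comparison takes no account of baseline differences that non-random allocation can produce.

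Under both readings the paired tests say nothing about one drug against the other. At stake is whether the secondary results support any statement about the treatment difference, and with what power.

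**Working it through.** The plan gives no design figure for these outcomes, so there is none to reproduce. **Inputs:** 64 women per group (the plan's 64, read as per group because it leads to a group size of 70) and the P<0.05 threshold. Correlations, shifts and imbalances are assumptions, because the documents give none. Simulations use normal data with unit SD at both times.

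**1. Mann-Whitney on baseline against 12-month values in one group.** With within-patient correlation ρ, the variance of the difference is smaller than the test assumes by a factor of about 1−ρ. The actual two-sided level is therefore about 2 × [1 − Φ(1.96/√(1−ρ))].

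- ρ = 0.3: 1.96/√0.7 = 2.34, level about 1.9% (simulated 2.1%).
- ρ = 0.5: 1.96/√0.5 = 2.77, level about 0.6% (simulated 0.5% to 0.8%).
- ρ = 0.8: 1.96/√0.2 = 4.38, level close to 0% (simulated 0.03% or less).

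Simulated power for a 0.3 SD shift, two-sided 5%, over several runs:

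| ρ | Mann-Whitney | Signed-rank |
|---|---|---|
| 0.3 | 35% to 37% | 49% to 50% |
| 0.5 | 33% to 34% | 63% to 65% |
| 0.8 | 26% to 28% | 95% to 96% |

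For a location shift the error is lost power, not false positives.

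**2. Mann-Whitney between groups.** On change scores with no baseline imbalance, its simulated size is 4.8% to 5.8%, so it holds its level. Now assume a 0.3 SD baseline imbalance and no treatment effect given baseline. The standard error of a group difference is SD × √(2/64) = 0.177 × SD. The expected group difference is 0.3ρ in 12-month values (SD 1) and 0.3(1−ρ) in size for changes (SD √(2(1−ρ))).

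- ρ = 0.5, 12-month values: 0.15/0.177 = 0.85 standard errors. Changes (SD 1): also 0.85. Simulated rejection is 13% for each.
- ρ = 0.7, 12-month values: 0.21/0.177 = 1.19. Changes (SD 0.775): 0.09/(0.775 × 0.177) = 0.66. Simulated rejection is about 20% and 10%.
- ANCOVA rejects in 4% to 6% of runs.

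Power for a true 0.4 SD effect, ρ = 0.5, no imbalance: the ANCOVA residual SD is √(1−0.25) = 0.866, its standard error 0.153, and 0.4/0.153 = 2.61. Unadjusted, 0.4/0.177 = 2.26. Simulated power is 72% for ANCOVA and 59% for Mann-Whitney.

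**3. One-sided paired t-tests within each group.** If both groups truly change by the same amount and each test has power p, exactly one group is significant with probability 2p(1−p): 2 × 0.8 × 0.2 = 32% at p = 0.8, and 50% at p = 0.5. In simulation this ran from 50% down to 2% for a mean change of 0.2 to 0.5 SD of the change. If the direction were chosen after seeing the data, a one-sided 0.05 threshold would act as 2 × 0.05 = 0.10 two-sided.

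**The case against.** The strongest reply is that the sentence refers only to differences and never says that both tests are applied before and after treatment. With two parallel groups, paired t-test within and Mann-Whitney between is at least as natural a reading, and then both tests are valid for what they do. This stands. A reader might infer that the plan prescribes invalid tests, or that Mann-Whitney is the wrong tool under any reading; the documents support neither.

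Other points that stand:

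- A change score already subtracts baseline. The false-rejection figures in step 2 assume that groups differing at baseline regress to a common mean. If baseline differences were stable over time, change scores would be the unbiased choice. Adjusting for the outcome's own baseline also leaves other confounding untouched.
- The contrast of about 95% with 27% power needs a correlation of 0.8; at 0.3 it is about 50% with 35% to 37%. The simulations use normal data, so they do not show that changes in skewed markers would be missed, and the same sentence also names a paired t-test for those variables.
- The plan states no rule that infers a treatment effect from significance in one group only. Step 3 shows what that inference would risk, not that it is planned.
- Times are not given explicitly for bone ALP, osteocalcin, PINP and CTX. That they have baseline values is inferred from their place in a paired-test list.

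The reply does not supply the missing assignment of tests to contrasts, give the one-sided tests a direction or provide a baseline-adjusted comparison.

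**Conclusion.** The point holds as an ambiguous and weak specification of the secondary analyses. On the within-group reading, Mann-Whitney ignores pairing and is very conservative: level about 2% to almost 0%, and power about 35% to 27% against about 50% to 95%, at assumed correlations of 0.3 to 0.8. On the between-group reading it is valid but unadjusted: 10% to 20% false rejection under an assumed 0.3 SD imbalance with no effect given baseline, and 59% against 72% power in the assumed 0.4 SD case. On either reading the paired tests are one-sided against P<0.05 with no direction and do not compare treatments.

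Because BMD is in the same list, a reader might also infer that the primary comparison is compromised. It is not: BMD change has its own independent t-test in the preceding sentence. The matter is worth correcting but is confined to secondary outcomes.

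**What to change.** For SF-36, Lysholm, turnover markers and laboratory results, define the treatment comparison as the two-sided group term from an ANCOVA of the 12-month value on its baseline, on the log scale for skewed markers. Report within-group changes descriptively; if a P value is wanted, use a two-sided paired t-test or Wilcoxon signed-rank test. Do not use Mann-Whitney on paired values. State the measurement times of bone ALP, osteocalcin, PINP and CTX.

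The cost is a little more analysis work with a standard model and no new data, provided that the turnover markers have baseline values. The document is dated April 2021, after the stated study period (November 2015 to December 2019), so if results have already been produced this is a reanalysis and should be labelled as such. Adjusting for an outcome's own baseline will not remove other confounding from non-random allocation, and the report should say so.
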